1 BACKGROUND AND RATIONALE

Globally, colorectal cancer (CRC) is the third most common cancer in men and women, with an estimated 1.4 million new cases and 694,000 deaths in 2012; the majority of which occur in developed countries. In Europe, CRC is the second most common cancer, with an estimated 447,136 new cases and 214,855 deaths in 2012.¹ Approximately one-quarter of patients with CRC have metastatic disease at the time of initial diagnosis and half of the patients develop metastatic disease following their initial diagnosis.²

Metastases in CRC can be synchronous (detected prior/during surgery of the primary tumor or within 3 to 12 months following initial intervention) or metachronous (discovered more than 1 year after surgical resection of the primary tumor). Synchronous metastases are usually associated with a locally advanced CRC following a greater metastatic burden and a poor outcome.¹⁸ The most frequently involved organs in metastatic CRC (mCRC) are the liver, peritoneum, lungs, bone and brain. The liver is often the single site of metastasis in CRC at the time of initial diagnosis (20% to 25% of cases) or after resection of the primary tumor (40% of cases).¹⁹ Peritoneal metastases are detected in 4% to 19% of patients after surgical resection of the primary tumor, and have survival rates of 5-24 months.²⁰ Lung metastases occur in 10% to 30% of patients at 5-60 months after resection of the primary tumor.²¹ The incidence of bone metastases in CRC varies from 6% to 10%, with a median time of detection of 11-21 months after resection of the primary tumor.²² Brain metastases occur in 2% to 12% of CRC patients during the course of the disease, with a median survival rate ranging from 2.8 to 6 months without surgery and from 6 to 10 months after metastatic resection.²³ Recent research suggests that certain gene mutations, such as Kirsten Rat Sarcoma Viral Oncogene (KRAS), B-Raf proto-oncogene (BRAF), phosphatidylinositol 3-kinase catalytic subunit (PIK3CA), and Neuroblastoma RAS viral oncogene homolog (NRAS) oncogenes, may affect the metastatic behavior of tumors and the patterns of metastatic spread.

Treatment options for mCRC patients

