The treatment combination resulted in a median overall survival of 9.0 months (95% confidence interval [CI] = 8.0–11.4 months) in patients treated with the triplet compared to 5.4 months (95% CI = 4.8–6.6 months) for the control regimens (hazard ratio = 0.52, 95% CI = 0.39–0.70; $P < .0001$). The objective response rate for the targeted triplet therapy was 26%, compared to 2% for the controls. The triplet combination was generally well tolerated with no unexpected toxicities. Grade 3 or higher adverse events were seen in 58% of patients on triplet treatment, 50% of those in the doublet group, and 61% of those in the standard therapy group.

50

Data from the BEACON CRC trial are being used to support regulatory approval of the triplet combination in BRAF V600E–mutant metastatic colorectal cancer, and BRAF inhibitor–based treatment has recently been included as a treatment option in the National Comprehensive Cancer Network© (NCCN©) Guidelines for colon and rectal cancers in the United States.

In light of the early clinical data of the Phase III BEACON CRC study, a Phase II, open label, single-arm, multi-center study, the ANCHOR CRC study, is currently ongoing to evaluate the antitumor activity of the Triplet combination of encorafenib, binimatinib and cetuximab by assessing the confirmed ORR in adult subjects with previously untreated BRAF^{V600E} mutant mCRC, where a total of 90 subjects will be enrolled and the study treatment will be administered in 28-day cycles until disease progression, unacceptable toxicity, withdrawal of consent, initiation of subsequent anticancer therapy or death. After discontinuation of the study treatment, subjects will be followed for survival until 1 year after the start of the treatment of the last subject enrolled.

STUDY RATIONALE

The presence of a BRAF^{V600E} mutation is considered a marker of poor prognosis in patients with mCRC, and findings from clinical trials have largely remained inconclusive regarding the efficacy of first-line treatment options for BRAF^{V600E} mutant mCRC patients. In the absence of a targeted/specific treatment for BRAF^{V600E} mutant mCRC, treatment practices can vary based on local practices and guidelines. There is, therefore, an unmet need to document the current practices for first-line treatment of BRAF^{V600E} mutant mCRC, and their effectiveness and safety in a real-world setting.

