3.3.6 Confounding variables

Multivariable analysis will be performed adjusting for baseline covariates in this study. Covariates of interest include patient demographics and clinical profile, and treatment history of CRC, which will be assessed before or at the time of mCRC diagnosis. The baseline covariates are summarized in Table 3.

Table 3 Study Covariates

Covariates	Definition
Age	Age in completed years at the time of first-line treatment for mCRC (will be computed from the date of birth and date of diagnosis of mCRC)
Gender	Male, female
Weight	Weight in kilograms
Height	Height in centimeters

Covariates	Definition
BMI (kg/m ²)	Calculated using weight and height values BMI categories: <18.5, 18.5 - <25, 25 - <30, 30 - <35, ≥35 and unknown/missing
Tests/investigations related to mCRC diagnosis/treatment	
 Records (along with the relevant test dates) of the radiologic, histologic and laboratory tests during the time of diagnosis and follow-up will be extracted based on available information in patient medical records. 
 Tumor Biomarker Assessments (tumor sample or ctDNA): BRAF; RAS; MSI; MMR Blood biomarker assessments: C-reactive protein; carcinoembryonic antigen; carbohydrate antigen 19-9
TNM stage at initial diagnosis	
 Tumor/node/metastasis (TNM) stage (I, II, III, IV) at the time of initial diagnosis of CRC will be abstracted based on available information in patient medical records.
Histology and location of the primary tumor at initial diagnosis	
 Histology at the time of initial diagnosis of CRC will be abstracted based on available information in patient medical records: 
 Adenocarcinoma Other carcinoma Location of the primary tumor: 
 colon left colon right colon transverse rectum
Metastasis status	Metastasis status will be abstracted based on available information in patient medical records: 
 Synchronous or Metachronous Location: Liver, lungs, lymph nodes, bone, peritoneum, CNS, other location(s), unknown Number of metastatic sites

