Treatment history	Prior medications/therapies for CRC (where available in patient medical records): 
 Radiation therapy: site of radiation, start and stop date, intent Chemoradiation: concurrent or sequential, regimen, start and stop date Surgery: date, location, intent
Comorbidity profile	Comorbidities of interest: ischemic cardiac disorder, congestive heart failure, peripheral vascular disease, cerebrovascular disease, chronic pulmonary disease, diabetes mellitus with end-organ damage, moderate or severe renal disease, moderate or severe liver disease, rheumatic or connective tissue disease, acquired immunodeficiency syndrome (AIDS), treated hypertension, heart rhythm disorder, others

Covariates	Definition
Performance status	
 • Performance status will be evaluated by ECOG: 
 ○ 0=Fully active, able to carry on all pre-disease performance without restriction ○ 1=Restricted in physically strenuous activity but ambulatory and able to carry out work of a light or sedentary nature, e.g., light house work, office work ○ 2=Ambulatory and capable of all self-care but unable to carry out any work activities. Up and about more than 50% of waking hours ○ 3=Capable of only limited self-care, confined to bed or chair more than 50% of waking hours ○ 4=Completely disabled. Cannot carry on any self-care. Totally confined to bed or chair 
ECOG performance status will be collected at mCRC diagnosis

Biological parameters	
 • Routine laboratory tests at the mCRC diagnosis

BMI: body mass index; BRAF: B-Raf proto-oncogene; CNS: central nervous system; CRC: colorectal cancer; CRP: C-reactive protein; ctDNA: Circulating tumor DNA; ECOG: Eastern Cooperative Oncology Group; LOT: line of therapy; mCRC: metastatic colorectal cancer; MSI: microsatellite instability; MMR: mismatch repair; TNM: Tumor, Node, Metastasis.

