3.4 DATA SOURCES AND COLLECTION

The source of collected data will be all elements that can constitute a reliable source of patient-level information and that are available at the site. This includes data available in the patients' medical charts (e.g., consultation notes, discharge summaries, laboratory test results, recorded prescription data and any other documentation of communication with other health care providers). The site investigator will be responsible for ensuring that all the required data is collected and entered into the eCRF.

The data collection schedule is presented in Table 4.

Table 4 Data Collection Schedule

Data collection	Date of enrollment/Dat a abstraction	Data at CRC/mCRC diagnosis/Initiation of first-line treatment	Data observational period ³	Discontinuation
Informed consent ¹ at NIS entry ² , where applicable	X			
Demographics (age at diagnosis, gender, weight, height)		X ⁴ ,		
Diagnosis details (date of diagnosis of CRC and mCRC, TNM stage, histology, primary tumor location)		X ^{4,5}		
Performance status: ECOG		X ⁴		
Comorbidities		X ⁴		
Metastasis details (location, number of metastatic sites)		X ⁴		
Test (tumor and blood biomarker assessment, radiological tests, colonoscopy, other laboratory tests)		X ⁶	X ⁶	
Local BRAF mutation testing (specimen type, date of specimen collected/received, date of results reported, and results with test type/name)		X ⁶		
Prior medications/therapies/procedures for treatment of CRC		X		
Systemic anti-cancer therapies for mCRC (agent name(s), start date and stop date, duration and number of treatment cycles, maintenance)			X ⁷	
Treatment alteration (e.g., switch, discontinuation, dose reduction); dates and reasons for treatment alteration			X ⁸	
Treatment response for each line of treatment treatment: type of response (CR, PR, PD); date recorded			X	
Survival status and date of death (if applicable)			X	
Cause of death (if applicable)			X	
Relevant AEs		X ⁸	X ⁸	X ⁸

1. Informed consent should be obtained prior to any data collection from the patient (or the patient's legally authorized representative), where required by local regulations.
2. Reason for non-participation, gender, age at diagnosis, first line treatments received (if available) and survival status will be collected in the NIS screening log for patients who will not consent to participate in this study, if local regulation permits.

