3.8 DATA ANALYSIS

3.8.1 General considerations

All computations and generation of tables, listings and data for figures will be performed using SAS® version 9.2 or higher (SAS Institute, Cary, NC, USA). Statistical analyses will be fully described in a written Statistical Analysis Plan (SAP), which will be prepared before database lock. The SAP will detail the most appropriate statistical methodology and analyses to be performed in accordance with the study design and objectives.

The Full Analysis Set (FAS) containing all patients who fulfil the eligibility criteria, will be used for this study. If a patient withdraws consent, the patient's data collected before the consent withdrawal will remain in the dataset. Patients in the FAS will also be included in the safety analysis set.

The study endpoints will be analyzed overall, by country and by pre-defined subgroup(s) of interest (e.g., age, gender, primary tumor location, number of metastatic organs). Further details will be provided in the SAP.

Analyses will be descriptive in nature, as no hypothesis will be tested. Data will be analyzed according to the complete case approach, where patients with missing data for relevant variable(s) will be excluded.

Categorical variables will be summarized by frequencies and percentages. Continuous variables will be summarized by descriptive statistics (mean, and standard deviation, median, 25th and 75th percentiles, minimum and maximum). The number of missing observations for each variable will also be reported.

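### Table 3, the stated covariate list, omits country, calendar year of first-line start and centre type, so any adjusted regimen hazard or odds ratio may keep residual confounding by place and time

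*Combined protocol and SAP*

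**What the plan says.** Section 3.3.6 of the protocol is headed as the section on confounding variables. It commits to adjustment: "Multivariable analysis will be performed adjusting for baseline covariates in this study". It gives the scope as "Covariates of interest include patient demographics and clinical profile, and treatment history of CRC" and points to Table 3 for the list.

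Table 3 covers age, gender, weight, height, BMI, tumour and blood biomarkers (including both MSI and MMR), TNM stage, histology and location of the primary, metastasis status, treatment history, comorbidity, ECOG and routine laboratory tests. The treatment-history row opens with "Prior medications/therapies for CRC (where available in patient medical records". It then itemises only radiation, surgery and "Chemoradiation: concurrent or sequential, regimen, start and stop date".

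Elsewhere the plan treats place as important:

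- The study rationale says that "treatment practices can vary based on local practices and guidelines".
- Section 3.1 plans eight countries and selects sites by centre type, size and practice.
- Section 3.8.1 says: "The study endpoints will be analyzed overall, by country and by pre-defined subgroup(s) of interest".

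Table 4 collects the start date of each systemic therapy and also "Prior medications/therapies/procedures for treatment of CRC". Section 3.8.3 says that Cox and logistic models may be used to adjust for predefined baseline covariates. Full detail is left to a separate SAP, to be written before database lock, whose text is not among the documents.

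**The concern.** A factor confounds a regimen comparison if it influences both which regimen a patient receives and how the patient fares. The protocol itself names local practice as a source of variation in treatment, yet its covariate list has no variable for where or when treatment began. If countries differ in regimen use and also in outcome for reasons that Table 3 does not capture, a model built on Table 3 would credit part of the country difference to the regimen.

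This matters because the exposure of interest in section 3.3.4 is first-line systemic therapy, and PFS, OS, response and treatment duration are to be described by regimen. The study rationale also says that the results will put a single-arm trial into context and may support health technology assessment submissions. A reader of such a submission is likely to take an adjusted HR between regimens as free of differences between countries.

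**Working it through.** **1. Table 3 against the rest of the protocol**

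| Factor | In Table 3? | Elsewhere in the protocol |
|---|---|---|
| Country | No | Local practice named in the rationale; by-country results in 3.8.1 |
| Year of first-line start | No | Derivable from the start date in Table 4; start window 2016 to 2018 |
| Centre type | No | Used for site selection in 3.1 |
| Prior systemic chemotherapy | Under the row heading, but not itemised | Prior medications collected in Table 4 |

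**2. The plan's own figure.** The only sample-size figure is the precision of regimen shares, 1.96 × √[p(1−p)/n]. With n = 300 it gives 2.47%, 3.39% and 4.53% for shares of 5%, 10% and 20%. These agree with Table 5, but they say nothing about adjusted models.

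**3. Crude illustration (assumed inputs).** Take two equal country groups with triplet use of 40% and 10% and no regimen effect. Triplet patients are then 0.40/0.50 = 80% from the first group. The others are 0.60/1.50 = 40% from the first group. With exponential survival the hazard is proportional to 1/median, so the apparent HR at the start of follow-up is

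(0.8/m1 + 0.2/m2) / (0.4/m1 + 0.6/m2).

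- Medians 15 and 10 months: 0.0733/0.0867 = 0.85
- Medians 14 and 11 months: 0.0753/0.0831 = 0.91
- Medians 13 and 12 months: 0.0782/0.0808 = 0.97

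A Cox model over the whole follow-up gives the same values to two decimals. Censoring was taken as uniform between 13 and 49 months, which are starts from January 2016 to December 2018 followed to 31 January 2020. The medians lie within the 10 to 15 months that section 1 gives for BRAF-mutant disease. The 40% and 10%, and the assignment of the survival gap to country, are assumptions.

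**4. Any omitted binary factor (assumed inputs).** The bias factor is [1 + p1(HR−1)] / [1 + p0(HR−1)], where p1 and p0 are the factor's prevalences in the two regimens.

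- Outcome HR 1.25, prevalence 45% against 55%: 1.1125/1.1375 = 0.98
- Outcome HR 2.0, prevalence 30% against 70%: 1.30/1.70 = 0.76

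**5. Scale against sampling error.** The expected proportion dying is 1 minus the average of exp(−ln2 × t/m) over t from 13 to 49 months. It is 0.851 for m = 10 and 0.733 for m = 15, or 255 and 220 deaths among 300. In step 3 the triplet share is 25%, so 75 against 225 patients. The 95% CI of the unadjusted HR then extends by a factor of exp[1.96 × √(1/63.8 + 1/191.4)] = 1.33 each way for m = 10. For m = 15 it is exp[1.96 × √(1/55.0 + 1/164.9)] = 1.36.

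**6. Cost in parameters.** Country as a covariate takes 7, year 2 and prior chemotherapy in three classes 2, so 11 in all. Dropping weight, height and one of MSI/MMR returns 3 (each counted as one parameter), leaving a net 8. Centre type adds 1 in a sensitivity model. Against 220 to 255 deaths, 11 parameters leave about 20 to 23 deaths each, before the other Table 3 covariates are counted. If complete-case analysis kept 180 patients (assumed), deaths fall to 132 to 153, or about 12 to 14 per added parameter.

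**The case against.** The strongest reply is that no regimen contrast has been promised. Section 3.8.1 calls the analyses descriptive, section 3.8.3 makes the models optional, and neither says that the HR is between regimens. Section 3.3.6 says only that covariates of interest include those listed, and the SAP could add others. This limits the point to any adjusted regimen result that is produced. It does not remove it: section 3.3.6 says without qualification that adjustment will be done, and a section on confounding presupposes an exposure and an outcome.

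The second reply is that the illustration has no Table 3 covariates in it. It shows crude bias, and part of any difference between countries in case mix would be removed by age, ECOG, tumour location and metastatic sites. The assumed bias is also smaller than the CI factor of 1.33 to 1.36. Both are correct. A wide interval hides bias without correcting it, but no figure here estimates what remains after adjustment.

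Three stronger readings are tempting, and the documents do not support them:

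- A reader might infer that prior adjuvant chemotherapy has been left out. The row heading, the scope statement in section 3.3.6 and Table 4 all cover it. What is missing is an itemised field with agents and dates.
- A reader might infer that country, centre, year and adjuvant therapy are the main drivers of regimen choice. The protocol supports local practice as a driver and is silent on the others. Plausible patient-level drivers are already in Table 3.
- From "Approximately one-quarter of patients with CRC have metastatic disease at the time of initial diagnosis and half of the patients develop metastatic disease" a reader might infer that 0.50/0.75 = 67% of patients, about 200 of 300, have metachronous disease and could have had adjuvant chemotherapy. Section 1 counts metastases found up to 12 months after the initial intervention as synchronous, and the fractions are for all colorectal cancer. Nothing says that every such patient had adjuvant chemotherapy.

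**Conclusion.** The point holds as a gap in the stated covariate list. Country, year of first-line start and centre type are absent, and the protocol's own rationale gives a reason to include place. The case for year is weaker: the documents report no trend over 2016 to 2018, but the variable costs little and can be derived from data already collected.

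Residual confounding of adjusted regimen HRs or odds ratios is possible, not demonstrated. It also needs a link between these factors and outcome after Table 3 adjustment, which the documents do not give, so its size cannot be computed. The crude range of about 0.85 to 0.97 rests on assumed regimen shares and survival gaps. The primary objective, a description of treatment patterns, is unaffected.

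One practical matter comes first. Sections 3.2.3.2 and 3.7 say that the patient number carries no indication of centre or country, and section 4.4 says that reports will not identify countries, while section 3.8.1 plans by-country analyses. A number without a country code does not exclude a separate country field, but the protocol does not say that one exists. Section 3.7 also has the enrolment record destroyed at database lock, so fields not secured by then may not be recoverable.

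**What to change.** Before database lock, in the SAP and where needed in the eCRF:

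1. Confirm that country is held as a database field, and reconcile sections 3.2.3.2, 3.7 and 4.4 with section 3.8.1. Record whether centre type is held.
2. State whether adjusted regimen contrasts are intended, and align the firm wording of section 3.3.6 with the optional wording of section 3.8.3.
3. Add country to the Cox and logistic models as a stratum or covariate, pooling small countries under a rule set in advance. Add year of first-line start (2016, 2017, 2018). Use centre type as a sensitivity adjustment if it is held.
4. Under the existing treatment-history row, itemise neoadjuvant and adjuvant systemic chemotherapy with agents and dates. Adjust for it as none, without oxaliplatin, or with oxaliplatin.
5. Use BMI alone in place of weight, height and BMI, and a single MSI/MMR variable.

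The cost is SAP wording, one itemised eCRF entry from the same charts and about 10 degrees of freedom. Some information is also lost: regimens with 5% to 20% of 300 patients number 15 to 60, or on average about 2 to 8 per country across eight countries. With stratification, a country that uses a single regimen contributes nothing to the contrast, which is the reason for pooling.

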3.4 DATA SOURCES AND COLLECTION

The source of collected data will be all elements that can constitute a reliable source of patient-level information and that are available at the site. This includes data available in the patients' medical charts (e.g., consultation notes, discharge summaries, laboratory test results, recorded prescription data and any other documentation of communication with other health care providers). The site investigator will be responsible for ensuring that all the required data is collected and entered into the eCRF.

The data collection schedule is presented in Table 4.

Table 4 Data Collection Schedule

Data collection	Date of enrollment/Dat a abstraction	Data at CRC/mCRC diagnosis/Initiation of first-line treatment	Data observational period ³	Discontinuation
Informed consent ¹ at NIS entry ² , where applicable	X			
Demographics (age at diagnosis, gender, weight, height)		X ⁴ ,		
Diagnosis details (date of diagnosis of CRC and mCRC, TNM stage, histology, primary tumor location)		X ^{4,5}		
Performance status: ECOG		X ⁴		
Comorbidities		X ⁴		
Metastasis details (location, number of metastatic sites)		X ⁴		
Test (tumor and blood biomarker assessment, radiological tests, colonoscopy, other laboratory tests)		X ⁶	X ⁶	
Local BRAF mutation testing (specimen type, date of specimen collected/received, date of results reported, and results with test type/name)		X ⁶		
Prior medications/therapies/procedures for treatment of CRC		X		
Systemic anti-cancer therapies for mCRC (agent name(s), start date and stop date, duration and number of treatment cycles, maintenance)			X ⁷	
Treatment alteration (e.g., switch, discontinuation, dose reduction); dates and reasons for treatment alteration			X ⁸	
Treatment response for each line of treatment treatment: type of response (CR, PR, PD); date recorded			X	
Survival status and date of death (if applicable)			X	
Cause of death (if applicable)			X	
Relevant AEs		X ⁸	X ⁸	X ⁸

1. Informed consent should be obtained prior to any data collection from the patient (or the patient's legally authorized representative), where required by local regulations.
2. Reason for non-participation, gender, age at diagnosis, first line treatments received (if available) and survival status will be collected in the NIS screening log for patients who will not consent to participate in this study, if local regulation permits.
3. Observational period: patients will be followed from the start of first-line treatment for mCRC and followed until the end of the observation period. Patients lost to follow-up will be censored at the date of their last available medical record or the date when they were last known to be alive.
4. Data to be collected at the time of mCRC diagnosis.
5. Data to be collected at the time of initial diagnosis of mCRC/CRC.
6. Information on routine laboratory tests will be collected at the time of mCRC diagnosis; information on other tests (including BRAF mutation) and assessments can be captured throughout the observation period.
7. Data on number of treatment cycles and maintenance therapy to be collected for first-line therapy only.
8. Data to be collected for first-line therapy only.

AE: adverse event; CR: complete response; CRC: colorectal cancer; ECOG: Eastern Cooperative Oncology Group; mCRC: metastatic colorectal cancer; NIS: non-interventional study; PD: progressive disease; PR: partial response; TNM: Tumor, Node, Metastasis.

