3.3.4 Exposure definition and measurement

This is a NIS of real-world treatment practices in the adult BRAF^{V600E} mutant mCRC patient population. This protocol does not recommend the use of any specific treatments, and no study medication will be provided as part of participation in the study.

The exposure of interest will be the first-line SACT (monotherapy, doublet therapy, or triplet therapy with or without a targeted therapy [either VEGF inhibitor or EGFR inhibitor]) for the treatment of BRAF^{V600E} mutant mCRC. Treatment patterns will be described by LOT.

Line of therapy will be defined as follows:

- First LOT: the start of first LOT will be defined as the first administration of SACT therapy after diagnosis of mCRC to the date of first documented disease progression
- Second and subsequent LOTs: mCRC treatment(s) received on or after the date of documented disease progression following previous LOT to the date of documented disease progression on or after the current LOT
- In the absence of information on disease progression, an algorithm will be specified in the SAP based on the specific treatment(s) received (stop and start dates), progression (as recorded in the patient medical record, including date), documented reasons for discontinuation of treatments and gap(s) between subsequent treatment regimens.

The exposure variables of interest are described in Table 1.

Table 1 Study Exposure

Exposure	Definition and Measurements
Systemic anti-cancer therapy (SACT) ¹ for mCRC	
 Details on SACT (by LOT) 
 LOT² (e.g., first, second, third, etc.) Type of treatment³ (i.e., monotherapy, doublet therapy, triplet therapy) Agents used 
 Chemotherapy regimens (e.g., FOLFOX, FOLFIRI, FOLFOXIRI) Targeted agents (e.g., bvacizumab, cetuximab, panitumumab) Duration of treatment: start date and stop date Date of documented progression Dates and reasons for treatment alteration (e.g., switch, discontinuation, dose escalation/reduction) Maintenance therapy (if any) of first line treatment: name of agent(s); start date and stop date Treatment response (as recorded in patient medical record by the treating physician) of first-line treatment of mCRC: type of response (CR, PR, PD); date recorded

¹ All SACT treatments received/prescribed for mCRC will be captured.

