Relevant Adverse events	
 Time to treatment cessation is defined as the length of time between initiation of first-line treatment and documented disease progression (or start of subsequent LOT, if disease progression is not well documented in patient medical record), treatment discontinuation or switch to another treatment (defined as change from 1 treatment regimen to another). Time to treatment cessation will be calculated from the date of initiation of LOT to the date of disease progression, treatment discontinuation or switch. Patients with no disease progression, treatment discontinuation or switch to another treatment will be censored at the earliest of: date of last medical record entry, last day of the observation period or date of death.
Cause of death (for deceased patients)	
 Information on relevant AEs during the study period will be collected based on information available in the patient medical records. Relevant AEs will be mapped into the (MedDRA) and grouped by SOC and PT. 
Relevant AEs are defined as AEs leading to first-line treatment switch, dose adaptation or discontinuation, or leading to death.

Reasons for treatment discontinuation or switch	
 The primary cause of death will be recorded as available in the medical record (cancer-related, non-cancer related, unknown/missing). Reasons for treatment alteration, defined as treatment interruptions, switches and discontinuation, will be collected at the end of each treatment, based on information available in the patient medical records.

¹ For patients in whom disease progression is not well documented, the start date of subsequent LOT will be considered instead of the date of disease progression. Detailed derivation of LOT will be provided in the SAP.

CR: complete response; ICD-10: International Classification of Diseases 10th Revision; mCRC: metastatic colorectal cancer; MedDRA: Medical Dictionary for Regulatory Activities; LOT: line of therapy; ORR: overall response rate; OS: overall survival; PD: progressive disease; PFS: progression free survival; PR: partial response; PT: preferred term; SOC: system organ class.

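### Table 4 collects reasons for ending treatment in first line only, although Tables 1 and 2 set no such limit and the line-of-treatment algorithm in 3.3.4 lists those reasons as an input

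*Combined protocol and SAP*

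**What the plan says.** Four places in the protocol bear on this.

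- **Section 3.4, Table 4.** The row "Treatment alteration (e.g., switch, discontinuation, dose reduction); dates and reasons for treatment alteration" is marked for the observation period with footnote 8, which reads "Data to be collected for first-line therapy only". The row for relevant adverse events carries the same footnote.
- **Section 3.3.5, Table 2.** Reasons for interruptions, switches and discontinuation "will be collected at the end of each treatment, based on information available in the patient medical records". No line is singled out.
- **Section 3.3.4, Table 1.** Dates and reasons for alteration appear among the systemic therapy details recorded by LOT. In the same cell, maintenance therapy and response are expressly tied to first line; the reasons are not. The synopsis data list follows the same pattern.
- **Section 3.3.4, line definitions.** After defining first and later lines by documented progression, the text adds: "In the absence of information on disease progression, an algorithm will be specified in the SAP". The stated inputs include "documented reasons for discontinuation of treatments and gap(s) between subsequent treatment regimens".

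**The concern.** Table 4 is the collection schedule, so an eCRF built from it would hold no reason for stopping after first line. Yet the algorithm is meant for patients whose progression is not documented, and in them the reason for stopping is one of the few signs that separates a change within a line from the start of a new one.

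The output at stake is exploratory endpoint 2 (sections 3.3.3 and 3.8.4), which reports agents and treatment duration in second and subsequent lines. If a later-line change for toxicity were taken as a new line, second-line duration would come out too short and the number of later lines too high. A rule that leans on gaps could also err the other way and merge two true lines.

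Timing adds weight. Sections 3.7 and 3.9 have the link between patient and record destroyed at database lock. Before lock the charts can still be consulted for a given record; afterwards they cannot.

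**Working it through.** The plan gives no figure for this point, so the check compares the texts.

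**1. Does the algorithm reach beyond first line?** The algorithm sentence is the third bullet in 3.3.4, after one bullet on first line and one on second and subsequent lines, and it names no line. With documented progression, a later line consists of "mCRC treatment(s) received on or after the date of documented disease progression following previous LOT". Without it, the algorithm is the only rule given for placing later boundaries. That it covers every line is therefore an inference from position and unrestricted wording, but it is the natural reading.

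**2. Which inputs exist in which line, under Table 4?**

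| Input named in 3.3.4 | First line | Later lines | Basis |
|---|---|---|---|
| Agents, start and stop dates | yes | yes | Table 4; footnote 7 limits only cycle counts and maintenance to first line |
| Recorded progression | where charted | where charted | Table 1, date of progression by LOT; Table 4, response including PD with date for each line |
| Gaps between regimens | yes | yes | follows from the dates |
| Reasons for discontinuation | yes | **no** | Table 4, footnote 8 |

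One of four inputs is missing, and only after first line. The response item for later lines rests on Table 4, since Table 1 ties response to first line.

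**3. Can the reason be recovered elsewhere?** Not from the adverse event data, because footnote 8 covers that row too.

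**4. Which boundaries are affected?** The reason for ending first line is collected, so the boundary between first and second line keeps all its inputs. The boundary between second and third line, and later ones, lose the reason. There is one exception. A site might label a regimen second line after a change without progression, and the algorithm might return that regimen to first line. The reason it ended would then be absent. Because the start of the next line stands in for progression in PFS when progression is poorly documented (sections 3.3.2 and 3.3.5), a secondary endpoint could be touched in such patients.

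**5. Can a size be computed?** It would need the number starting second line, the share with poorly documented progression, the share changed for toxicity, and the algorithm's treatment of such changes. The documents give none of these.

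**The case against.** The strongest reply is that footnote 8 fits the objectives. The only endpoint that reports reasons, exploratory endpoint 1, covers the end of first-line treatment, and its objective concerns patients starting first line. On that view Table 2 means each treatment within first line, and the slip lies in Tables 1 and 2. This reading is possible and would settle the conflict with Table 2. It leaves the by-line listing in Table 1 and the named algorithm input, so some text must change whichever way the sponsor decides. It also means that 3.3.4 should not be read as a collection rule: it lists inputs and does not itself require an end-reason for every line.

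Three stronger inferences are tempting and are not supported:

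- *A reader might infer that later-line toxicity switches will be scored as new lines.* The algorithm is deferred to the SAP and is not in the supplied text. Misassignment is possible, not established.
- *A reader might infer that only dates and gaps remain.* Agent names are collected for all lines, and so is response, including dated progression where charted. Only patients with poorly documented progression are exposed.
- *A reader might put a percentage on the overstatement of third-line use.* Every input would be assumed. Such a sum would also go wrong if it counted all misassigned patients as excess, because those who later truly reach third line add nothing to the number reaching it.

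It is also fair that the study is descriptive, tests no hypothesis, and is affected here mainly in an exploratory output.

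**Conclusion.** The inconsistency stands in current text. As scheduled, Table 4 withholds from later lines an input that 3.3.4 names for assigning lines. This could bias second-line duration and the number of later lines in exploratory endpoint 2, among patients whose progression is poorly documented. The size cannot be stated.

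The conclusion assumes that the algorithm applies to all lines and that the eCRF follows Table 4. The primary endpoint, PFS and time to treatment cessation are largely unaffected, apart from the relabelling case described above. The point deserves correction because the remedy is small and the information cannot be retrieved after lock, not because a main result is in danger.

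**What to change.** **Preferred.** Split the treatment-alteration row of Table 4. Lift footnote 8 from the reason for ending or switching treatment, so that one coded end-reason is collected for every line of systemic therapy. Keep dose changes, interruptions and relevant adverse events first-line only. Stop dates are already collected for all lines, so no new date is needed. The cost is one coded field per later line and a small amount of extra abstraction from charts already open. It is cheapest before data entry starts (planned for April 2020 in Table 6) and must be done before lock (planned for November 2020).

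**If footnote 8 is kept.** Limit the reasons entries in Tables 1 and 2 to first line. State in the SAP that later lines are assigned without reasons for stopping. Add a sensitivity analysis of exploratory endpoint 2 under alternative line-change rules, for example with a change of agent without recorded progression counted first as the same line and then as a new one. This needs no new data, but it shows the uncertainty without reducing it.
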